1.4.3. Phase I Experience with Carfilzomib as a Monotherapy

The results of a Phase I clinical trial, PX-171-002, testing carfilzomib in subjects with relapsed/refractory hematologic malignancies, was recently reported.⁴³ During the dose escalation portion of the trial, 36 subjects received carfilzomib on Days 1, 2, 8, 9, 15, and 16 of a 28-day cycle. Subjects with multiple myeloma (MM), non-Hodgkin's lymphoma (NHL), Waldenström's macroglobulinemia, and Hodgkin's lymphoma (HL) were enrolled in the study.

No dose limiting toxicities (DLTs) were observed in the initial seven cohorts (doses ranged from 1.2 mg/m² to 15 mg/m²) of 3 subjects each. At the 20 mg/m² dose level, 1 of 8 patients had a Grade 3 renal failure at Cycle 1, Day 2 which was considered possibly related to study drug and lasted for 6 days. The patient continued on study for the remainder of Cycle 1 before having disease progression. At the 27 mg/m² dose level, 1 of 6 subjects experienced a DLT during Cycle 1, consisting of severe hypoxia with pulmonary infiltrates following Day 2 of dosing. In subjects where the 27 mg/m² dose was efficacious, a "first dose effect" was seen that included a

constellation of findings that appeared to be the clinical sequelae of rapid tumor lysis syndrome (TLS) and/or cytokine release. This effect was notable for fever, chills, and/or rigors occurring during the evening following the first day of infusion. On the second day, three of 5 subjects with multiple myeloma experienced an increase in creatinine to Grade 2 (including the subject with the DLT). This elevation was rapidly reversible and all three subjects were rechallenged with carfilzomib without recurrence of the events. Interestingly, all 3 subjects had a rapid decline in serum and/or urine M-protein levels; 2 subjects achieved a PR and the third subject achieved a minimal response (MR). There were no consistent changes in potassium, calcium, phosphorous, or uric acid levels although some increases in LDH and other markers of tumor lysis were noted. Because of the possible TLS and reversible creatinine elevations, hydration and very-low dose dexamethasone prophylaxis were instituted in subsequent studies and have essentially eliminated clinically significant TLS/creatinine elevations and the other “first-dose” effects.

Hematologic toxicities were primarily mild or moderate. The thrombocytopenia reported with carfilzomib is cyclical and similar to that reported with bortezomib. The cause and kinetics of the thrombocytopenia following treatment are different from those of standard cytotoxic agents. To maximize the likely benefit of carfilzomib, subjects with thrombocytopenia should be supported as clinically indicated rather than having treatment reduced due to thrombocytopenia.

Of the 36 evaluable patients enrolled in PX-171-002, 20 had MM.⁴³ Four MM patients achieved a partial response (PR), 1 of 2 at the 15 mg/m² dose, 1 of 6 at the 20 mg/m² dose, and two of five at the 27 mg/m² dose. The responses have been rapid in onset, beginning in some subjects after 1 – 2 doses. The duration of response (DOR) ranged from 134 to 392 days. The minimal effective dose was 15 mg/m² wherein > 80% proteasome inhibition in peripheral blood and mononuclear cells was observed 1 hour after dosing. The median number of prior therapies for subjects on this trial was five, and responses were seen in subjects who had relapsed from (including some refractory to) bortezomib and/or immunomodulatory agents. Stable disease also occurred in 4 NHL and 5 MM subjects, with subjects on therapy for up to 409 days. Such prolonged therapy, at “full” twice-weekly doses, is not possible with bortezomib. These results led to the initiation of 2 Phase II studies.

1.4.4. Phase II Experience with Carfilzomib as a Monotherapy

Two Phase II clinical studies are ongoing with carfilzomib in MM patients, PX-171-003-A0 (N = 46) in relapsed and refractory MM and PX-171-004 (N = 39) in relapsed MM. In both studies, patients were dosed with 20 mg/m² on Days 1, 2, 8, 9, 15, and 16 on a 28 day schedule. In these studies there were 4 cases of suspected or documented TLS prior to institution of the prophylaxis guidelines. Since these guidelines were implemented, no further cases of TLS have been reported including in > 350 additional patients with relapsed or refractory MM treated in ongoing Phase II studies. In both studies, the most common adverse events were fatigue, anemia, thrombocytopenia (primarily cyclical), gastrointestinal, and dyspnea. Almost all were Grade 1 or Grade 2. There were reported cases of increased in serum creatinine that were primarily < Grade 2 and were transient, rapidly reversible, and non-cumulative. A very low rate of treatment-emergent peripheral neuropathy, 2.2% Grade 3/4, was observed in PX-171-003-A0 despite the fact that 78% of patients had Grade 1/2 neuropathy upon study entry.⁴⁴

The response rate in PX-171-003-A0 was 18% PR, 7% MR and 41% SD in these patients that entered the study with progressive disease and were refractory to their most recent therapy, often including bortezomib and/or an immunomodulatory drug (usually lenalidomide). The median time to progression on the PX-171-003-A0 study was 5.1 months with a DOR of 7.4 months (mean follow up of 7.6 months).⁴⁴

A “stepped up” dosing schedule, referred to as 20/27 mg/m², has subsequently been incorporated into the PX-171-003 study (referred to as PX-171-003-A1) in order to maximize the clinical benefit of carfilzomib. Patients receive 20 mg/m² for the first cycle and 27 mg/m² thereafter. The study completed enrollment of 266 patients by the end of 2009 and may form the basis for an accelerated approval NDA filing in the future. To date, this dosing schedule has been well tolerated.⁴³ An independent Safety Oversight Group (SOG) evaluated the safety data from the 40 of 250 patients to be enrolled on the 20/27 schedules and agreed that the trial should proceed without modification. No cases of TLS were observed and rates of BUN and creatinine elevation dropped sharply, with Grade 3/4 renal impairment dropping to 2.2% in A1 (from 15% in A0), most likely due to hydration and very low dose dexamethasone. The other most common adverse events were similar to the A0 portion of the study. Treatment-emergent peripheral neuropathy remains low on this portion of the study with 15% Grade 1/2 and one (0.7%) Grade 3/4 events reported to date on PX-171-003-A1.⁴⁴ In addition, anemia rates in the PX-171-003-A1 (higher dose) were lower than those reported in the PX-171-003-A0 portion of the study, possibly indicating that the higher dose of carfilzomib is achieving better clearing of neoplastic cells in the bone marrow allowing superior normal marrow reconstitution. Rates of thrombocytopenia and neutropenia were similar in the 2 cohorts, with Grade 3 neutropenia in approximately 5% without any Grade 4 neutropenia to date.⁴⁴

In PX-171-004, a first cohort of patients received 20 mg/m². The subset of patients (N = 54) that had not seen bortezomib had an ORR of 46% (2% CR, 9% VGPR and 35% PR), while the bortezomib treated patients (N = 33) had an ORR of 18% (3% CR, 3% VGPR and 12% PR).⁴⁵ The median TTP was 7.6 and 5.3 months in these 2 groups, respectively. Thus, carfilzomib can induce very high levels of response in patients who have not previously been treated with bortezomib and, even in bortezomib-treated patients, substantial anti-tumor activity is observed. Of note, disease control (PR + MR + SD) was achieved in approximately 65% of patients with progressive MM entering the study. Patients on these studies have been treated for > 12 cycles with good tolerability and no cumulative toxicity (e.g., bone marrow, severe fatigue, or neuropathy) have not been observed.

The protocol was amended to allow patients to increase to 27 mg/m² in Cycle 2 or later based on tolerability, similar to that used in PX-171-003-A1. Further information about the Phase II studies is presented in the Investigator’s Brochure.

1.4.5. Experience with Carfilzomib in Combination with Lenalidomide and Dexamethasone

PX-171-006 is an ongoing Phase Ib study in patients with relapsed multiple myeloma in which carfilzomib is administered in combination with lenalidomide (Revlimid®) and dexamethasone. “Low-dose” dexamethasone 40 mg/day is given on Days 1, 8, 15, and 22 in all cases.

Carfilzomib is administered IV on Days 1, 2, 8, 9, 15, and 16; lenalidomide is administered PO on Days 1 through 21. Enrollment has closed in this study, and no MTD was reached. The maximum per protocol doses of carfilzomib (27 mg/m²) with lenalidomide 25 mg and low dose dexamethasone are being used.⁴⁶ After 8 patients tolerated these doses well, an additional 44 patients were enrolled in an “expansion” cohort at this level, and this regimen is being taken into Phase III in study PX-171-009.

To date, 40 patients were treated in Cohorts 1 - 6 and 44 in the Cohort 6 expansion. 27/32 patients in cohorts 1 - 5 are evaluable for safety and 29/32 for response. Patients were heavily pre-treated; 72% received prior BTZ and 87.5% received prior LEN or thalidomide (Thal). 47% of patients were refractory to their last therapy (typically lenalidomide + high dose dexamethasone; > 84% of patients had a history of neuropathy with 67% BTZ- or Thal-related. No treatment emergent fatigue, neuropathy, or thrombotic events \geq Grade 3 were observed. Hematological AEs \geq Grade 3 (thrombocytopenia [n = 6], anemia [n = 4], and neutropenia [n = 6]) were reversible. 4 patients had drug-related SAEs as follows: transient Grade 3 sinus bradycardia, Grade 3 upper respiratory tract infection, febrile neutropenia, and Grade 3 diarrhea + Grade 3 urinary infection. ORR and CBR for the 29 evaluable patients are 59% and 72%, respectively. Response data is shown in the table below. Initial responses improved with continued therapy, (up to 18 cycles). Median duration of response has not been reached (median follow-up 5.2 months). No dose-limiting toxicities or deaths attributed to study treatment have been observed. Several patients have completed the study (in the lower dose cohorts) after 18 cycles and are continuing in an extension study. Updated efficacy data are presented in the following table:

Table 1. CRd: Cohorts 1–5 (Carfilzomib: 15 to 20 mg/m²; LEN: 10 to 25 mg)

Response	Relapsed (n = 16)	Refractory (n = 13)	Overall (n = 29)
\geq CR/nCR	5 (31)	1 (8)	6 (21)
\geq VGPR	7 (44)	4 (31)	11 (38)
\geq PR	9 (56)	8 (62)	17 (59)
\geq MR	11 (67)	10 (77)	21 (72)

Together, these results suggest that carfilzomib, lenalidomide, and low-dose dexamethasone (CRd) in combination are active and well tolerated and that there are no significant overlapping toxicities (in the dose ranges tested). Importantly, lenalidomide-associated neutropenia and thrombocytopenia do not appear to be exacerbated by concurrent treatment with carfilzomib, even up to 27 mg/m², suggesting that carfilzomib will combine well with other anti-cancer agents.

2. RATIONALE

Current standard salvage chemotherapy regimens (e.g., R-ICE, R-DHAP, etc.) used prior to HDC-ASCR in patients with relapsed/refractory DLBCL yield suboptimal outcomes. The ORR and CR response rate following salvage therapy with R-ICE or RDHAP is 63% and 38%

respectively. Moreover, the 3-year progression-free survival of relapsed/refractory DLBCL patients initially treated with R-CHOP and then salvage R-ICE or R-DHAP and HDC-ASCT is only 30%. The incorporation of active novel agents into the management of relapsed/refractory DLBCL is needed in an attempt to improve clinical outcomes.

A group of Roswell Park investigators has demonstrated that the ubiquitin-proteasome system plays an important role in the development of rituximab-chemotherapy resistance in B-cell lymphoma. Moreover, targeting the proteasome system with pharmacological inhibitors has resulted in significant anti-tumor activity in relapsed/refractory DLBCL. While the combination of bortezomib and systemic chemotherapy is currently being studied in patients with relapsed/refractory DLBCL, bortezomib is limited by its toxicity profile. Carfilzomib is a more potent and better tolerated proteasome inhibitor when compared to bortezomib. The study is seeking to determine the maximum tolerable doses of carfilzomib when administered in combination with the R-ICE chemotherapy regimen in relapsed/refractory DLBCL patients who are ASCT-eligible.

2.1. Dose Rationale

Preliminary data suggest that carfilzomib as a single agent can produce substantial response rates in myeloma and B-cell lymphoma subjects across a variety of dosing cohorts. Responses were seen over a wide therapeutic window, from 15 mg/m² to 27 mg/m². Maximum proteasome inhibition was seen at doses 11 mg/m² and higher in whole blood samples taken 1 hour after the first dose. The final analysis of the human pharmacokinetic (PK) data is ongoing but appears to be rapid and similar to the results from the animal studies. Carfilzomib is rapidly cleared from plasma with an elimination half-life of < 60 minutes at the 20 mg/m² dose. Large, single arm studies of the 27 mg/m² dose are ongoing and suggest that this dose is very well tolerated with patients being treated for > 10 cycles without cumulative toxicities.

By the end of 2009, 269 patients with relapsed and refractory multiple myeloma have been enrolled in the PX-171-003-A1 study. The goal of dose escalating to 27 mg/m² beginning with Cycle 2 is to improve ORR, DOR, and TTP. In multiple preclinical studies, the tolerability of carfilzomib in rats has been shown to be significantly higher when administered as a 30 minutes infusion as compared to a rapid IV bolus. Toxicities observed with IV bolus injection of carfilzomib *above the MTD* at a dose of 48 mg/m² include evidence of prerenal azotemia (transient increases in BUN > creatinine) as well as lethargy, piloerection, dyspnea, and gastrointestinal bleeding. Notably, death occurred in approximately 50% of animals at 48 mg/m² when carfilzomib was given as a bolus. Administration of the same dose (48 mg/m²) as a 30 minutes continuous infusion was well tolerated, with no changes in BUN and creatinine and substantially reduced signs of lethargy, piloerection, or dyspnea. Moreover, all animals in the infusion treatment groups survived. The only toxicity observed following infusion of carfilzomib for 30 minutes was gastrointestinal bleeding. The reduced toxicity seen with dosing by infusion may reflect the reduced C_{max} of carfilzomib vs that with bolus dosing.⁴⁷ Inhibition of the pharmacological target of carfilzomib (the chymotrypsin-like activity of the proteasome) was equivalent in the bolus and infusion treatment groups.

In the clinic, the MTD of carfilzomib has not been reached in the multiple myeloma (MM) setting, particularly when administered as a 30-minute infusion. 27 mg/m² of carfilzomib (bolus administration over 2 - 10 minutes) is well tolerated in MM patients overall and can be tolerated for > 12 cycles in late stage MM patients with substantial comorbidities.

A Phase I dose escalation study (PX-171-007) of single agent carfilzomib administered is ongoing and over 65 patients with solid tumors had received therapy in the initial Phase II portion of the study at 36 mg/m² (bolus administration over 2 - 10 minutes). A review of the tolerability of 36 mg/m² carfilzomib in these patients indicates that this regimen was very well tolerated with only one DLT (fatigue) and an overall adverse event profile similar to that seen with the 27 mg/m² carfilzomib experience with bolus dosing (see IB for details). Three patients completed > 12 cycles of therapy at 36 mg/m² with no evidence of cumulative toxicity. There were no significant DLTs observed; the majority of discontinuations on the study were due to progressive disease. Because of the long-term tolerability carfilzomib, the Phase Ib portion of this study was reopened, and a separate arm for multiple myeloma was added.

In the PX-171-007 trial, more recently patients have been treated with carfilzomib given as a 30-minute infusion in order to potentially minimize Cmax-related infusion events. The protocol was amended and doses of 20/36 (20 mg/m² given on Day 1 and Day 2 of Cycle 1 only; followed by 36 mg/m² for all subsequent doses), 20/45, 20/56 mg/m² and so forth are being investigated. Doses of 20/56 mg/m² are currently being given in 2 separate cohorts of patients with advanced MM and advanced solid tumors; the lower doses were well tolerated. Preliminary tolerability information at this dose level (20/56 mg/m²) indicated that it is reasonably well tolerated with minimal infusion reactions. In some cases at 20/56 mg/m², dexamethasone was increased from 4 mg/dose to 8 mg with the 56 mg/m² doses in order to reduce fevers and hypotension. As of March 20, 2010, 7 patients have received 20/56 mg/m² and are tolerating it. Patients with advanced, refractory MM being treated at 36 mg/m² and 45 mg/m² have shown very good tolerability (> 6 months in some cases) with documented minimal and partial responses in these heavily pretreated patients. These data indicate that carfilzomib 30-minute infusion can be given at very high levels, with > 95% inhibition of blood proteasome levels achievable and with (at least) acute tolerability. All protocols using ≥ 36 mg/m² carfilzomib are now administering the drug as a 30-minute infusion.

In addition to the above observations, a Phase I study of carfilzomib in patients with relapsed and refractory multiple myeloma was reported in abstract form at the 2009 American Society of Hematology meeting which demonstrated that carfilzomib can be safely administered to patients with substantial renal impairment (CrCL < 30, including patients on dialysis) without dose adjustment.⁴⁸ These data indicate that carfilzomib does not exacerbate underlying renal dysfunction, and confirm the “pre-renal” etiology of the BUN/creatinine elevations observed with IV bolus carfilzomib.

3. OBJECTIVES

3.1. Phase I Primary Objectives

- To estimate the maximum tolerated dose (MTD) and examine the dose-limiting toxicities of carfilzomib when administered in combination with rituximab, ifosfamide, carboplatin, and etoposide (C-R-ICE) in patients with relapsed/refractory DLBCL.
- To assess the toxicity of dose regimen using the CTEP NCI Common Terminology Criteria for Adverse Events (CTCAE Version 4.0).

3.2. Phase Ib Primary Objectives (Expansion cohort)

- To evaluate the safety of carfilzomib (given at maximum tolerated dose [MTD] as determined in Phase I of this study) in combination with R-ICE salvage therapy in relapsed/refractory DLBCL patients.
- To achieve an overall response rate (CR and PR) of 70% after 3 cycles of C-R-ICE in patients between the ages of 18 to 75 with relapsed/refractory CD20-positive DLBCL previously treated with rituximab-based immunochemotherapy (e.g., R-CHOP, R-EPOCH, R-HyperCVAD, etc.) induction.

3.3. Secondary Objectives

- To determine the feasibility of successful mobilization of autologous stem cells (i.e., minimum of 2×10^6 CD34+ cells/kg should be collected) to be used for ASCT (if applicable).
- To determine toxicities associated with C-R-ICE salvage therapy.
- To determine the TTP, PFS, and OS followed by ASCT (if applicable); Disease-free survival in CR patients.
- To determine the pharmacokinetics/pharmacodynamics relationship between carfilzomib's degree of proteasome inhibition and response rate along with the time course of thrombocytopenia.
- To study differences in clinical outcomes between GCB and non-GCB relapsed/refractory DLBCL following therapy with carfilzomib and R-ICE.

[figure not shown]
Correlative translational research studies to include: phenotypic/genotypic analysis and functional activity (i.e., ADCC and CMC) of patient's peripheral blood mononuclear "effector" cells (PBMC), as well as ex vivo analysis of sensitivity of primary tumor cells to various combinations of carfilzomib versus Bortezomib +/- rituximab; enzymatic assay for chymotrypsin-like activity to determine the degree of proteasome inhibition in primary DLBCL patient samples and patient PBMC specimens; explorative analysis to identify potential factors predictive of response to therapy will be performed (as part of an NIH-supported R01 grant: R01 CA136907-0A1; PI: [name]).

4. METHODOLOGY

4.1. Study Design

This is an open-label, non-randomized, multicenter, dose-escalation Phase I, followed by Phase Ib expansion study of carfilzomib in combination with R-ICE regimen in relapsed/refractory DLBCL patients. Based on the results of the Phase I portion of the study, the Phase Ib dose will be at Dose Level 6. The study schema is depicted in **Figure 6**.

Figure 6. Treatment Plan Schema

Subjects will be treated on an inpatient and outpatient basis. All subjects will meet the inclusion and exclusion criteria summarized in **Section 5.1** and **Section 5.2** prior to enrollment in this study.

4.2. Target Accrual and Study Duration

A maximum of 21 patients for Phase I and 9 patients for the Phase Ib expansion part of this trial will be enrolled at Roswell Park and Network Sites (For Phase Ib only). The number of subjects required is a function of a currently unknown dose-toxicity relationship. Accrual is expected to take up to 10 years.

5. SUBJECT SELECTION

5.1. Inclusion Criteria

To be included in this study, subjects must meet the following criteria:

5.1.1 Disease Specific

- Histological confirmation of relapsed/refractory CD20 positive diffuse large B-cell lymphoma. Network sites must submit slides to Roswell Park for Central Review and confirmation.
- Ann Arbor Stage I – Stage IV DLBCL at the time of relapsed/refractory disease to be eligible.
- Measurable or assessable disease is required. Measurable tumor size (at least one node measuring 2.25 cm^2 in bidimensional measurement) per CT scan, other radiological study, and/or physical exam.

5.1.2 Prior Treatment

- Patients must have received at least 1 prior rituximab-based immunochemotherapy (e.g., R-CHOP, R-EPOCH, etc.).
- ≥ 2 weeks since major surgery.
- Patients must not have any significant toxicity associated with prior surgery, radiation therapy, chemotherapy, or immunotherapy, per PI discretion

5.1.3 Demographic

- Age ≥ 18 years and ≤ 75 years of age.
- Life expectancy ≥ 3 months.
- Karnofsky Score (KS) ≥ 50 (**Appendix B**).

5.1.4 Laboratory

- Adequate hepatic function, with serum ALT/AST ≤ 3.5 times the upper limit of normal in the absence of a history of Gilbert's disease (or pattern consistent with Gilbert's), within 14 days prior to starting therapy.

- Adequate bone marrow reserve (If patient has cytopenias due to bone marrow involvement, these requirements are not applicable):
 - Absolute neutrophil count (ANC) $\geq 1.0 \times 10^9/L$ within 14 days prior to starting therapy.
 - Hemoglobin $\geq 8 \text{ g/dL}$ (80 g/L) within 14 days prior to starting therapy (subjects may be receiving red blood cell [RBC] transfusions in accordance with institutional guidelines).
 - Platelet count $\geq 50 \times 10^9/L$ ($\geq 20 \times 10^9/L$ if lymphoma involvement in the pre-treatment bone marrow is found) within 14 days prior to starting therapy
- Patients must have a serum creatinine of $\leq 1.5 \text{ mg/dL}$; if creatinine $> 1.5 \text{ mg/dL}$ creatinine clearance must be $> 60 \text{ mL/min}$ within 7 days prior to treatment either measured or calculated using a standard Cockcroft and Gault formula. Refer to **Appendix C**.

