Participant Name: (Network sites use participant initials): _____

Medical Record No.: (Network sites use participant initials) _____

Title: **Phase I Study of Carfilzomib Plus Rituximab Plus Ifosfamide Plus Carboplatin Plus Etoposide (C-R-ICE) in Patients with Relapsed/Refractory Diffuse Large B-cell Lymphoma (DLBCL)**

INCLUSION CRITERIA				
Yes	No	N/A	All answers must be "YES or "N/A" for patient enrollment.	Date
			1. Histological confirmation of relapsed/refractory CD20 positive diffuse large B-cell lymphoma. Network sites must submit slides to Roswell Park for Central Review and confirmation.	
			2. Ann Arbor Stage I – Stage IV DLBCL at the time of relapsed/refractory disease to be eligible	
			3. Measurable or assessable disease is required. Measurable tumor size (at least one node measuring 2.25 cm ² in bidimensional measurement) per CT scan, other radiological study, and/or physical exam.	
			4. Patients must have received at least 1 prior rituximab-based immunochemotherapy (e.g., R-CHOP, R-EPOCH, etc.).	
			5. ≥ 2 weeks since major surgery.	
			6. Patients must not have any significant toxicity associated with prior surgery, radiation therapy, chemotherapy, or immunotherapy, per PI discretion	
			7. Age ≥ 18 years and ≤ 75 years of age.	
			8. Life expectancy ≥ 3 months.	
			9. Karnofsky Score (KS) ≥ 50 (Appendix B).	
			10. Adequate hepatic function, with serum ALT/AST ≤ 3.5 times the upper limit of normal in the absence of a history of Gilbert's disease (or pattern consistent with Gilbert's), within 14 days prior to starting therapy.	

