			11. Adequate bone marrow reserve (If patient has cytopenias due to bone marrow involvement, these requirements are not applicable): 
• Absolute neutrophil count (ANC) ≥ 1.0 × 10⁹/L within 14 days prior to starting therapy.• Hemoglobin ≥ 8 g/dL (80 g/L) within 14 days prior to starting therapy (subjects may be receiving red blood cell [RBC] transfusions in accordance with institutional guidelines).• Platelet count ≥ 50 × 10⁹/L (≥ 20 × 10⁹/L if lymphoma involvement in the pre-treatment bone marrow is found) within 14 days prior to	

INCLUSION CRITERIA

Yes	No	N/A	All answers must be "YES or "N/A" for patient enrollment.	Date
			starting therapy.	
			12. Patients must have a serum creatinine of ≤ 1.5 mg/dL; if creatinine > 1.5 mg/dL creatinine clearance must be > 60 mL/min within 7 days prior to treatment either measured or calculated using a standard Cockcroft and Gault formula. Refer to Appendix C .	
			13. Written informed consent in accordance with federal, local, and institutional guidelines.	
			14. Females of childbearing potential (FCBP) must agree to ongoing pregnancy testing and to practice contraception. Should a woman become pregnant or suspect she is pregnant while she or her partner is participating in this study, she should inform her treating physician immediately.	
			15. Male subjects must agree to practice contraception.	
			16. No known hypersensitivity to murine products.	
			17. Patients must have normal baseline cardiac function based upon echocardiogram or gated blood pool scan (MUGA) with an ejection fraction $\geq 50\%$.	
			18. Patients who test positive for HepC Ab are eligible provided all of the following criteria are met: a) bilirubin ≤ 2 x upper limit of normal; b) ALT/AST ≤ 3 x upper limit of normal; and c) clinical evaluation to rule out cirrhosis.	

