5.1.5 Medical/Ethical

- Written informed consent in accordance with federal, local, and institutional guidelines.
- Females of childbearing potential (FCBP) must agree to ongoing pregnancy testing and to practice contraception. Should a woman become pregnant or suspect she is pregnant while she or her partner is participating in this study, she should inform her treating physician immediately.
- Male subjects must agree to practice contraception.
- No known hypersensitivity to murine products.
- Patients must have normal baseline cardiac function based upon echocardiogram or gated blood pool scan (MUGA) with an ejection fraction $\geq 50\%$.
- Patients who test positive for Hepatitis C Antibody are eligible provided all of the following criteria are met: a) bilirubin $\leq 2 \times$ upper limit of normal; b) ALT/AST $\leq 3 \times$ upper limit of normal; and c) clinical evaluation to rule out cirrhosis.
- Specific guidelines will be follow regarding inclusion of relapsed/refractory DLBCL based on Hepatitis B serological testing as follow:
 - HBsAg negative, HBcAb negative, HBsAb positive patients are eligible.
 - Patients who test positive for HBsAg are ineligible (regardless of other Hepatitis B serologies).
 - Patients with HBsAg negative, but HBcAb positive (regardless of HBsAb status) should have a HBV DNA testing done and protocol eligibility determined as follow:
 - If HBV DNA is positive, the subject will be excluded from the study.

- If HBV DNA is negative, the subject may be included but must undergo at least every 2 months HBV DNA PCR testing from the start of treatment throughout the duration the treatment course.

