7.3. Criteria for Retreatment

The following laboratory parameters must be met before starting Cycles 2 and Cycle 3:

- Begin subsequent cycles no sooner than Day 22 but no later than Day 36 (If a subject is delayed beyond Day 36, contact the Principle Investigator or designee from Roswell Park)
- ANC \geq 1000/ μ L without G-CSF
- Platelets \geq 50,000/ μ L
- Serum creatinine \leq 2.0 mg/dL
- Total bilirubin \leq 2.0 mg/dL (unless due to disease involvement with DLBCL or Gilbert's syndrome).

Serum chemistry values, including creatinine, must be obtained (within 24 hours) and reviewed prior to each dose of carfilzomib. Carfilzomib must be held for subjects with a CrCL $<$ 30 mL/min at any time during study participation. Subjects with active or suspected infection of any kind that required systemic treatment should not be dosed with carfilzomib until the infection has resolved and if being treated with anti-infective, the course of antibiotics has been completed.

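### The entry liver criterion ties the Gilbert's qualifier to ALT/AST and sets no bilirubin limit for hepatitis C-negative patients, while Section 7.3 limits bilirubin only from Cycle 2 onward

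*Combined protocol and SAP*

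**What the plan says.** **Entry.** Section 5.1.4 requires "Adequate hepatic function, with serum ALT/AST ≤ 3.5 times the upper limit of normal in the absence of a history of Gilbert's disease". Checklist item 10 has the same requirement, with the qualifier running "in the absence of a history of Gilbert's disease (or pattern consistent with Gilbert's), within 14 days prior to starting therapy". Neither place gives a bilirubin number.

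**Entry, hepatitis C only.** Section 5.1.5 says "Patients who test positive for Hepatitis C Antibody are eligible provided all of the following criteria are met", and lists bilirubin ≤ 2 x ULN, ALT/AST ≤ 3 x ULN and a clinical evaluation for cirrhosis. Checklist item 18 matches. This is the only numeric bilirubin limit at entry; no exclusion criterion in Section 5.3 mentions bilirubin.

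**Retreatment.** Section 7.3 opens: "The following laboratory parameters must be met before starting Cycles 2 and Cycle 3". Its list includes total bilirubin ≤ 2.0 mg/dL, "unless due to disease involvement with DLBCL or Gilbert's syndrome".

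**Other controls.** Sections 7.3 and 8.1 both state: "Serum chemistry values, including creatinine, must be obtained (within 24 hours) and reviewed prior to each dose of carfilzomib". Section 8.2 adds that Day 1 results must be judged acceptable before carfilzomib is given. Section 7.4.2.7 holds carfilzomib for a liver abnormality of Grade 3 or higher. It also says that use in hepatic impairment has not been characterized.

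**The concern.** There are two linked problems in one sentence.

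First, the protocol's own Section 7.3 treats Gilbert's as a reason for a raised bilirubin, yet the entry criterion attaches it to transaminases. There the wording has two readings with opposite effects, and the checklist allows either a yes or a not-applicable answer. Two sites could therefore score the same patient differently.

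Second, the entry criterion has no bilirubin number for most patients. The first exposure to the combination is thus the one cycle without a numeric bilirubin screen.

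What is at stake is patient safety at first dose and consistent eligibility decisions. Section 4.2 opens Phase Ib to network sites, and the network instructions in Appendix E allow no exceptions to eligibility criteria, so entry is meant to work by rule.

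**Working it through.** No sample size, power or error rate enters this point. The check sets the laboratory rules side by side.

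| Parameter | Entry (5.1.4) | Before Cycles 2 and 3 (7.3) |
|---|---|---|
| ALT/AST | ≤ 3.5 x ULN, with Gilbert's qualifier | none |
| Total bilirubin | none (≤ 2 x ULN if hepatitis C-positive, 5.1.5) | ≤ 2.0 mg/dL, with Gilbert's/DLBCL exception |
| Hemoglobin | ≥ 8 g/dL | none |
| ANC | ≥ 1.0 x 10⁹/L = 1000/µL | ≥ 1000/µL without G-CSF |
| Platelets | ≥ 50 x 10⁹/L = 50,000/µL | ≥ 50,000/µL |
| Creatinine | ≤ 1.5 mg/dL, or CrCL > 60 mL/min if above | ≤ 2.0 mg/dL |

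The entry ANC, hemoglobin and platelet limits are waived or lowered for marrow involvement.

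**Step 1: the numeric route into Cycle 1.** Take a hepatitis C-negative patient with ALT/AST ≤ 3.5 x ULN and, for illustration, total bilirubin of 2.5 mg/dL from neither Gilbert's nor DLBCL. The only numeric liver criterion at entry is ALT/AST, and it is met.

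**Step 2: the same value before Cycle 2.** If bilirubin is unchanged, 2.5 > 2.0 mg/dL and no exception applies, so Section 7.3 is failed. Section 8.4 allows at most 3 cycles, so a numeric bilirubin limit precedes 2 of 3.

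**Step 3: the two readings of the qualifier.**
- Reading A: the ALT/AST cap applies only to patients without Gilbert's. A hepatitis C-negative Gilbert's patient then has no numeric ALT/AST cap.
- Reading B: absence of Gilbert's is part of the requirement. A Gilbert's patient is then ineligible, which sits badly with Section 7.3 making an allowance for Gilbert's at retreatment.

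**Step 4: how much the table shows.** Of the four laboratory parameters in Section 7.3, three have an entry number and bilirubin does not. Counted the other way, two of the five entry parameters (ALT/AST and hemoglobin) have no counterpart in Section 7.3. The lists are not mirror images, so the count locates the omission and does not measure risk.

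**Step 5: what the other controls catch.**
- The adequate-function wording, the bar on significant prior-treatment toxicity (5.1.2) and the exclusion for serious medical conditions (5.3) carry no bilirubin number.
- The pre-dose review applies from Cycle 1. The example thresholds for withholding a dose in Section 8.2 concern tumor lysis (creatinine, LDH, uric acid, phosphate, potassium, calcium) and do not include bilirubin.
- The Grade 3 hold is graded. Table 3 (note 9) has bilirubin drawn on Days 1, 2, 8 and 9, so the hold can act within Cycle 1. It is an on-treatment rule and not an entry screen.

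**The case against.** The strongest reply is that entry and retreatment rules may differ by design. The protocol uses transaminases as its liver marker at entry and bilirubin later, and it also drops hemoglobin at retreatment. On this view an investigator facing an unexplained bilirubin above 2.0 mg/dL must still find liver function adequate and the laboratory results acceptable before the first carfilzomib dose. Section 14.2 places rituximab on Day 3 of Cycle 1, so that review comes before it as well. A graded hold then operates during the cycle. The fix itself keeps an exception that needs judgement, and at entry every patient has active DLBCL to which a raised bilirubin might be attributed.

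Much of this stands. These controls make it unlikely that many patients would slip through, and the exception remains a matter of judgement. But none of them gives a bilirubin number before first dose, and none resolves the two readings of the Gilbert's wording.

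A reader might also infer more than the text supports:
- *That liver-impaired patients enter unprotected.* They do not: the controls above apply, and no exposed patient is shown.
- *That the reported hepatic failures demonstrate a carfilzomib liver risk at raised bilirubin.* Section 7.4.2.7 reports three cases, two of which preceded death from end-stage myeloma progression, and it describes raised transaminases as infrequent. Section 6.3 says ifosfamide is activated in the liver but states no bilirubin-related risk.
- *That a bilirubin limit was deleted by mistake.* The pattern is compatible with that, but the documents do not say so, and the point does not depend on it.

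**Conclusion.** The point holds as a cheap improvement of low-to-moderate severity. As written, the Gilbert's qualifier is attached to ALT/AST and is ambiguous there, and hepatitis C-negative patients face no numeric bilirubin limit before Cycle 1, against ≤ 2.0 mg/dL before Cycles 2 and 3.

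The worked case assumes ALT/AST within limits, a cause other than Gilbert's or DLBCL, and a bilirubin that stays above 2.0 mg/dL. The documents do not say how many patients fit this. The number is probably small, since patients positive for HBsAg or HBV DNA are already excluded and hepatitis C-positive patients have their own cap. A change reaching only Phase Ib would apply to the 9 additional patients (Section 13.1.2) and any replacements; that is the reach of the rule, not a count of patients at risk.

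It would be wrong to infer that the response estimate, the 80.1% power or the 4.8% type I error is affected. Nothing in the documents links this criterion to those figures.

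**What to change.** In Section 5.1.4 and checklist item 10, require within 14 days before starting therapy:

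- (a) ALT/AST ≤ 3.5 x ULN, with no Gilbert's qualifier;
- (b) total bilirubin ≤ 2.0 mg/dL unless due to Gilbert's syndrome or DLBCL involvement, as in Section 7.3.

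Leave the hepatitis C limits in Section 5.1.5 and item 18 unchanged as additional requirements.

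**Cost.** The same edit in two places, with IRB approval under Section 17.1. No new test is needed: bilirubin shares the ALT/AST row of Table 3 and is already drawn before study.

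**Downsides.**
- A few patients are newly excluded: those with raised bilirubin from other causes, and Gilbert's patients with ALT/AST above 3.5 x ULN.
- The Gilbert's/DLBCL exception still needs judgement and has no ceiling, as in Section 7.3.
- Phase Ib patients would enter under a slightly tighter criterion than the Phase I patients with whom Sections 13.1.2 and 13.5 pool them. The report should say so.
- If the sponsor meant to bar Gilbert's patients, this wording would admit those with ALT/AST ≤ 3.5 x ULN. Section 7.3 suggests that was not the intent, but the sponsor should confirm it.
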